## 6 Study methodology

### 6.1 Prior and concomitant treatment(s)

An antibiotic prophylaxis is not obligatory due to the minimal surgical intervention.

For prohibited medication, see Exclusion Criteria section 5.3.3.2.

### 6.2 Demographics and other baseline characteristics

- Date of birth
- Sex
- Relevant medical and surgical history
- Medication at entry and during the study
- Nicotine use
- Oral examination including dentition of opposing jaw
- Edentulous period

- Reason for edentulism
- Bone quantity and quality (Visit 3)

### 6.3 Assessments of outcome variables

#### 6.3.1 Primary outcome variable

Implant survival rate

##### 6.3.1.1 Assessment of primary outcome variable

Implant survival will be evaluated clinically and radiographically by counting the number of implants remaining *in situ*. Any implant that has been removed or lost after implant placement (Visit 3) will be considered a failure, whatever the reason for removal/loss.

Implant survival rate will be analyzed on an implant level (i.e. percent of survived implants) as well as subject level (i.e. percentage of subjects with no lost implants).

#### 6.3.2 Secondary outcome variables

##### 6.3.2.1 Secondary outcome variable(s)

- Implant stability
- Marginal Bone Level alterations
- Soft tissue response (Plaque, PPD, BoP)
- OHIP-14
- Implant success
- Prosthetic survival
- Prosthetic success
- Number of avoided augmentations

##### 6.3.2.2 Assessment of secondary outcome variable(s)

###### – *Implant stability*

Implant stability will be evaluated clinically/manually at implant placement (primary stability) and at abutment surgery and recorded as yes/no.

###### – *Marginal Bone Level alterations*

Bone level response will be evaluated from intra-oral radiographs. To ensure good quality and reproducibility between the examinations, the below instructions must be followed:

- Standardized long-cone parallel technique should be used
- Film holders should be used
- The radiographic beam should be perpendicular to the implant and film
- The threaded profile of the marginal portion of the implant, both mesially and distally, must be clearly visible.
- If pathology around the implant is suspected, supplementary periapical x-rays should be taken.
- Double film and/or digital radiographs may be used and a hard copy or electronic copy of the image will always be retained on site for future reference.
- ***Radiographs must be marked with subject id, visit no, date and implant positions*** before uploading/sending them to DENTSPLY Implants. No subject names or birth dates should be visible on the radiographs.

The radiographs will be sent for central evaluation to a radiologist who is independent from the investigational group and DENTSPLY Implants. The radiologist will measure and record the

distance from a reference point on the implant to the most coronal bone-to-implant contact on the mesial and distal aspect of the implant. Peri-implant radiolucency will be registered as present or absent. The reference point is defined as the implant shoulder.

The mean marginal bone levels will be calculated for each implant as well as for each subject and used for further analysis. The alteration in the marginal bone level from baseline (Visit 8, Prosthetic Restoration) to each time point will be calculated.

- ***Soft tissue response (Plaque, PPD and BoP)***

Plaque will be recorded as presence or absence of plaque by visual inspection on four surfaces at each implant site (mesially, distally, buccally and lingually). PPD and BoP will be evaluated at the same four surfaces around the implant, by using a periodontal probe. PPD will be measured as the distance from the mucosal margin to the bottom of the probeable pocket in mm. BoP will be recorded as presence or absence of bleeding when probing to the bottom of the pocket.

- ***OHIP-14***

Patient satisfaction will be evaluated using the Oral Health Impact Profile 14 (OHIP-14). The questionnaire will be filled in by the subjects before and after treatment with implants.

OHIP-14 includes seven domains and is therefore able to cover a wide range of possible oral health problems that may have an impact on quality of life. The domains are: functional limitation, pain, psychological discomfort, physical disability, psychological disability, social disability and handicap. OHIP attempts to measure both the frequency and severity of oral problems on functional and psychosocial well-being. An example of an OHIP statement is "Have you had to interrupt meals because of problems with your teeth, mouth or dentures". Responses are based on a Likert scale (i.e., 0 = never, 1 = hardly ever, 2 = occasionally, 3 = fairly often, 4 = very often).

- ***Implant success***

Implant success will be evaluated as defined by the ICOI Pisa Consensus Conference 2008 [35]. An implant will be considered successful if all of the following criteria are fulfilled:

- Implant still in place
- No mobility
- No pain or tenderness upon function
- <2 mm marginal bone loss from initial surgery to 5-year follow-up visit
- No history of exudates

- ***Prosthetic survival***

A prosthetic restoration will be considered a *survivor* if the original restoration is still in place at the follow-up visit, regardless of its condition.

- ***Prosthetic success***

A prosthetic restoration will be considered as successful if it has remained unchanged and there has been no need of technical repair during the observation period.

The occurrence of any technical repair of the prosthesis or any biological complications related to the prosthesis will be registered and reported as ADEs (section 6.4.1.2).

- ***Number of avoided augmentations***

The proportion of augmentations avoided by using six 6.6 mm implants instead of six 8.0 mm implants will be virtually evaluated by using the SIMPLANT file generated from the CBCT at Visit 2. First, six regions of interest will be defined in SIMPLANT by indicating the mesial and distal borders of the canine, premolar and molar regions on both left and right side. An evaluator, independent from the investigational group and DENTSPLY Implants, will then make a surgical planning with six 6.6 mm implants placed at the pre-defined canine, premolar and molar regions and count the number of sites that would need augmentation. The evaluator will then repeat this

procedure but now use six 8.0 mm implants for the planning. If necessary, the evaluator will be allowed to exceed the region borders slightly when doing the surgical planning, in order to achieve maximal bone amount (to reflect the real situation).

The difference in number of needed augmentations for the 8.0 mm implants and the 6.6 mm implants divided by the number of needed augmentations for the 8.0 mm implants will represent the proportion of augmentations avoided by using the 6.6 mm implant.

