### 5.1.2 Visit 2, Pre-surgical planning

A CBCT (Cone Beam Computed Tomography, a type of Digital Volume Tomography) will be performed as a reliable diagnostic tool for an exact planning and realization of implant insertion.

The CBCT will be used to determine that there is adequate height and width of bone to allow implant placement of six 6.6 mm implants and to ensure a sufficient oral and vestibular bone lamella width of at least 1.5 mm. The jaw should have an appropriate width of 5.5 mm in the implant area (implant diameter 3.5 mm + 2x1.0 mm).

Data from the CBCT will also be used for evaluating the number of avoided augmentations by using the 6.6 implants instead of the 8.0 mm implants in the SIMPLANT software system for 3D planning.

*Clinical Work-Flow:*

- Prepare a scan prosthesis by rebasing the existing prosthesis. Make 8 small, superficial cavities in the prosthesis' gingiva. Fill each cavity with a SIMPLANT Dual Scan Marker dipped in radiolucent resin. Let the resin cure. For further instructions, see SIMPLANT manual 'How to fabricate a scan prosthesis for the dual scan procedure'
- CBCT with scan prosthesis
- CBCT DICOM data transferred to SIMPLANT
- SIMPLANT file used by Investigator for bone related surgical planning. The Investigator will plan for placement of 6 short 6.6 mm implants in the canine, premolar and molar regions on both sides (one implant in each of the six regions). Caution should be taken to find the most optimal implant positions with regard to mesio-distal dimensions to assure placement in maximal bone amount available.
- Copy of SIMPLANT file sent to Evaluator for assessment of number of avoided augmentations when using 6.6 mm implants compared to 8.0 mm implants
- Oral health-related quality of life (OHIP-14) to be filled out by the subject

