### 10.5 Statistical analysis during the course of the study

Partial clean file is planned to be declared when all subjects have completed:

- Visit 2 (CBCT) – data will be used for publication describing no. of avoided augmentations by using 6.6 mm implants instead of 8 mm implants (virtually evaluated in SIMPLANT file from CBCT taken before implant placement).
- Visit 10 (1-year follow-up) – data will be used for 1-year follow-up publication.
- Visit 12 (3-year follow-up) – data will be used for 3-year follow-up publication.

Data base lock will take place and total clean file will be declared when all subjects have completed:

- Visit 14 (5-year follow-up) – data will be used for 5-year follow-up publication.

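### The virtual comparison plans 6.6 mm first and 8.0 mm second in every jaw, which leaves the avoided-augmentation result open to an order or carry-over bias of unknown size and sign

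*Combined protocol and SAP*

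**What the plan says.** Section 6.3.2.2 (Number of avoided augmentations) sets out the procedure. Before any planning, "First, six regions of interest will be defined in SIMPLANT by indicating the mesial and distal borders" of the canine, premolar and molar regions on each side. "An evaluator, independent from the investigational group and DENTSPLY Implants", must then "make a surgical planning with six 6.6 mm implants placed at the pre-defined canine, premolar and molar regions" and count the sites that would need augmentation. The same evaluator next repeats the "procedure but now use six 8.0 mm implants for the planning". If needed, "the evaluator will be allowed to exceed the region borders slightly when doing the surgical planning", so as to reach maximal bone. The difference between the two counts "divided by the number of needed augmentations for the 8.0 mm implants will represent the proportion of augmentations avoided".

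Section 5.1.2 describes where the file comes from. The investigator uses the SIMPLANT file to plan the six 6.6 mm implants for surgery, and the next relevant step reads "Copy of SIMPLANT file sent to Evaluator for assessment of number of avoided augmentations". It is not stated whether the investigator's plan is removed from that copy.

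Section 10.3 lists avoidance of augmentations as a secondary objective with a confidence interval only. Section 10.5 gives it a separate data cut after Visit 2, whose "data will be used for publication describing no. of avoided augmentations". Section 7.8 also plans an article on it.

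**The concern.** Every jaw is planned for 6.6 mm first and for 8.0 mm second, by someone who has just finished the first plan. Any effect of being the second plan therefore falls entirely on the 8.0 mm count, and the data cannot separate it from the effect of length.

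There are two plausible routes, and they work in opposite directions:

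- **Carry-over of positions.** If positions chosen for 6.6 mm are reused, a site may be scored as needing augmentation at 8.0 mm although a fresh search would have found adequate bone nearby. This raises the 8.0 mm count and favours the 6.6 mm implant.
- **Familiarity with the scan.** On a second pass the evaluator knows the jaw better and may find an adequate 8.0 mm position that would otherwise have been missed. This lowers the 8.0 mm count and works against the 6.6 mm implant.

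This is the trial's only comparison of the two lengths. Section 1.2 rejects a randomised 8 mm control group and puts this virtual comparison in its place. An order effect could not be detected or corrected once the readings are done.

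**Working it through.** **What the plan provides.** It states no expected rate, sample size, power or precision for this endpoint, so there is no planned figure to reproduce. The primary-endpoint sample size in section 10.4 does not bear on it.

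**Is the order varied or the first plan hidden?** Sections 5.1.2 and 6.3.2.2 contain no random or alternating order, no separation of sessions, no removal of the first plan and no removal of the investigator's plan. Section 6.3.2.2 also gives no numerical rule for when a site needs augmentation, and the permitted excursion beyond the borders is not quantified. The evaluator therefore has some discretion.

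**How an order effect reaches the result.** Let A6.6 and A8.0 be the numbers of sites judged to need augmentation at each length. The planned ratio is (A8.0 − A6.6)/A8.0 = 1 − A6.6/A8.0. The avoided count, which sections 1.2 and 10.5 refer to, is A8.0 − A6.6. If the second plan's count is shifted by a fraction e, the fixed order gives a ratio of 1 − A6.6/[A8.0(1+e)] and a count of A8.0(1+e) − A6.6. The count moves one-for-one with A8.0.

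**Illustration.** Sites: 56 × 6 = 336, from the planned number of implanted subjects. The counts and e = ±10% are assumptions.

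| Case | A6.6 | A8.0 | Ratio without order effect | Ratio at e = −10% / +10% | Shift (points) | Avoided count and shift |
|---|---|---|---|---|---|---|
| a | 0 | 134 | 100% | 100% / 100% | 0 | 134 ± 13.4 (10.0%) |
| b | 10 | 134 | 92.5% | 91.7% / 93.2% | −0.8 / +0.7 | 124 ± 13.4 (10.8%) |
| c | 34 | 134 | 74.6% | 71.8% / 76.9% | −2.8 / +2.3 | 100 ± 13.4 (13.4%) |
| d | 34 | 67 | 49.3% | 43.6% / 53.9% | −5.6 / +4.6 | 33 ± 6.7 (20.3%) |

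Example, case c at +10%: 1 − 34/147.4 = 76.9%, against 1 − 34/134 = 74.6%.

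**What randomising the order alone would do.** With half the jaws in each order:

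- *Same proportional effect on whichever plan is second.* Both counts are multiplied by (1 + e/2), so the ratio is unbiased.
- *Only the 8.0 mm plan affected when second.* The ratio becomes 1 − A6.6/[A8.0(1 + e/2)]. Case c shifts by −1.3 / +1.2 points and case d by −2.7 / +2.4, about half the fixed-order shift. The shift in the count halves exactly (case c: 13.4 to 6.7 sites).
- *Same additive number of sites, d, on whichever plan is second.* The count difference is unbiased but the ratio is not. In case c with d = 7, the fixed order gives 1 − 34/141 = 75.9% (+1.3 points) and balanced order gives 1 − 37.5/137.5 = 72.7% (−1.9 points).

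The second pattern fits carry-over of positions best. A position adequate for 8.0 mm should also be adequate for 6.6 mm (assuming equal diameter, since the 8.0 mm diameter is not stated), but the reverse need not hold.

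**The case against.** The strongest reply is that nothing shows a bias. Repeating the procedure reads as a second full planning, and no sentence says that 6.6 mm positions are kept. The regions are fixed before either plan, the evaluator is independent of investigators and sponsor, and the border allowance serves maximal bone for either length. A position chosen for maximal bone at 6.6 mm will often be a good one at 8.0 mm too. All of this stands and limits the room for an order effect. None of it removes the confounding of order with length.

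A reader might infer that the order inflates the 8.0 mm count and so favours the sponsor's implant. The documents do not support that: the sign is open, because familiarity with the scan pulls the other way. Nor do they show that the evaluator sees the investigator's plan; they only fail to say that it is removed.

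It is also fair to say that the ratio may be insensitive. Eligibility requires bone height of at least 7 mm, and the same scan is used to check that six 6.6 mm implants fit. A6.6 may therefore be near zero in implanted subjects, and the ratio near 100% whatever A8.0 is (case a). That protects the ratio but not the avoided count, which still moves by 10% in case a.

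Finally, section 10.3 rests all conclusions on the primary objective, so the trial's main conclusion is untouched. That stands.

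**Conclusion.** The point holds as a potential, unquantified order or carry-over bias in a secondary endpoint that has its own publication. The fixed order and the absence of any step to hide earlier plans are plain from the text; the size and sign of any effect are not. The illustrated range, 0 to 5.6 points on the ratio and about 10% to 20% on the avoided count, rests on assumed counts and an assumed 10% shift. It shows sensitivity and is not an estimate.

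A reader might also infer that randomising the order would by itself balance the bias. That is true of the ratio only if the effect is the same proportion in both orders. A one-directional carry-over would be about halved, and an equal additive effect would leave the ratio biased. This is a low-cost improvement to the design, not an error or contradiction in the plan.

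**What to change.** Amend section 6.3.2.2, and the matching file-transfer step in section 5.1.2, before the readings are made:

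1. Start each plan from a clean SIMPLANT file showing only the six region borders, with the investigator's plan and the evaluator's first plan removed.
2. Do the two plans for a jaw in separate sessions.
3. Randomise per subject which length is planned first.
4. Report both counts, the avoided count and the ratio by planning order as a check. A difference in the 8.0 mm count between the two orders would point to an order effect.

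Steps 1 and 2 act on the carry-over itself, and steps 3 and 4 make any remaining order effect visible. The cost is a short randomisation list, a few sentences in the plan, file handling, and a second session per jaw. No extra evaluator, scan or plan is needed.

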## 10.2 Description of analysis sets

The study will be analyzed using a Safety (S) and an Intention-to-Treat (ITT) population approach. The S analysis set will consist of all included subjects who have been treated with implants. ITT analysis set will consist of all subjects fulfilling the inclusion criteria, none of the exclusion criteria and have had their implants installed as planned. Treatment efficacy related conclusions will be based on the results from the ITT analysis.

All subject data will be included in subject data listings.

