## 10.3 Method of statistical analysis in relation to objectives

If nothing else is stated, descriptive statistics will be given for each variable in the study and p-values may be complemented by confidence intervals as appropriate.

All p-values presented will be two-sided. A p-value less than 5% will be called “statistically significant” but all conclusions will be based on the primary objective and hence multiplicity is accounted for even though careful interpretations are necessary as multiple tests are performed. No formal adjustment for multiplicity will be applied and nominal p-values will be presented. All confidence interval will be two-sided and 95%.

When calculating p-values a non-parametric statistical approach will be applied because of the nature of the data. Confidence interval will be calculated using distribution assumptions.

The primary objective will be analysed using the exact Binomial test and a parametric confidence interval for the true proportion of implants surviving will be presented

The safety profile will be analysed using descriptive statistics only.

The planned statistical methods for the efficacy evaluation is presented by objective below:

Primary Objective	Corresponding Primary Outcome Variable	Statistical Method
Implant survival	Implant in situ during study	The exact Binomial test and a parametric confidence interval for the true proportion of implants surviving will be presented

Secondary Objective(s)	Corresponding Secondary Outcome Variable(s)	Statistical Method
Implant stability	Stability	A parametric confidence interval for the true proportion of implants with stability = “yes” will be presented
Bone tissue response	Marginal Bone Level (MBL)	The change over time will be tested using the Wilcoxon signed rank test and a parametric confidence interval presented.
Soft tissue response	Plaque, Probing Pocket Depth (PPD) and Bleeding on Probing (BoP)	The change over time will be tested using the Wilcoxon signed rank test and a parametric confidence interval presented.
Patient reported outcomes	OHIP-14	The change over time will be tested using the Wilcoxon signed rank test and a parametric confidence interval presented.

Secondary Objective(s)	Corresponding Secondary Outcome Variable(s)	Statistical Method

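### Avoided augmentations: no analysis set is named, and if ITT is used the ratio will tend to exceed that in all scanned subjects whenever any are excluded for bone

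*Combined protocol and SAP*

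**What the plan says.** **Outcome.** Under Number of avoided augmentations in 6.3.2.2, an independent evaluator plans six 6.6 mm and then six 8.0 mm implants on the Visit 2 CBCT and counts the sites needing augmentation each time. The difference is "divided by the number of needed augmentations for the 8.0 mm implants will represent the proportion of augmentations avoided". Section 10.3 adds a parametric confidence interval. Neither place names an analysis set.

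**Pointing to ITT.** The table in 10.3 that holds this outcome is introduced with "The planned statistical methods for the efficacy evaluation is presented by objective below". Section 10.2 states: "Treatment efficacy related conclusions will be based on the results from the ITT analysis". ITT membership requires eligibility and implants placed according to plan.

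**Pointing to all scanned subjects.** The Visit 2 work-flow in 5.1.2 has "Copy of SIMPLANT file sent to Evaluator for assessment of number of avoided augmentations", with no later eligibility filter. Section 10.5 plans a partial clean file once all subjects have completed Visit 2, and says "data will be used for publication describing no. of avoided augmentations by using 6.6 mm implants instead of 8 mm implants".

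**Selection.** The same CBCT establishes that there is "adequate height and width of bone to allow implant placement of six 6.6 mm implants" (5.1.2). The bone minimums of 7 mm height and 5.5 mm width must be met by Visit 3 (5.3.3.1). Section 5.5.3 foresees enrolled subjects who leave before surgery because they do not meet the criteria.

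**Criterion.** Section 6.3.2.2 does not say when a site needs augmentation. On width, 5.1.2 gives both a "sufficient oral and vestibular bone lamella width of at least 1.5 mm" and "implant diameter 3.5 mm + 2x1.0 mm".

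**Unit.** Section 10.4 assumes implants to be independent and makes them the statistical unit.

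**The concern.** The virtual comparison is the study's only contrast of 6.6 mm with 8.0 mm implants. Section 1.2 offers it in place of a randomised control, and it has its own planned publication. The two candidate sets answer different questions: augmentations avoided among people who could be treated with six 6.6 mm implants, or among everyone who reached 3D planning. Sites short of bone at 6.6 mm are what ITT tends to remove, and they are also what keeps the ratio below 1. A reader given one percentage with no stated set or criterion cannot tell which question it answers.

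Separately, sites in one jaw are likely to resemble each other, and the denominator is itself a random count. An interval that treats the 8.0 mm augmentation sites as a fixed number of independent trials would then claim more precision than the data hold.

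**Working it through.** The plan states no expected value or precision for this outcome, so there is no figure of its own to reproduce. Its sample size (304 implants, 51 evaluable and 56 treated subjects, 10.4) concerns implant survival only.

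**1. Direction.** Let A8.0 and A6.6 be the numbers of sites needing augmentation at each length, and R = (A8.0 − A6.6)/A8.0. Let w be the share of all A8.0 sites that belong to ITT subjects. Then

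R_all = w·R_ITT + (1 − w)·R_excluded, so R_ITT − R_all = (1 − w)·(R_ITT − R_excluded).

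The gap is zero if nobody is excluded (w = 1). It is positive when excluded subjects have the lower ratio. That is expected if the evaluator's reading tracks the eligibility reading, since a subject excluded for bone then has at least one site counted in A6.6. A site too narrow for both lengths adds to the denominator and nothing to the numerator.

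**2. Size by share excluded (assumed counts).** Take 56 ITT subjects, each with two sites needing augmentation at 8.0 mm and none at 6.6 mm: A8.0 = 112 and R_ITT = 1.00. Add n excluded subjects, with (A8.0, A6.6) per subject equal to (3, 1) or (5, 3).

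| n excluded | share of scanned | R_all with (3, 1) | R_all with (5, 3) |
|---|---|---|---|
| 0 | 0% | 1.00 | 1.00 |
| 3 | 3/59 = 5% | 118/121 = 0.98 | 118/127 = 0.93 |
| 6 | 6/62 = 10% | 124/130 = 0.95 | 124/142 = 0.87 |
| 14 | 14/70 = 20% | 140/154 = 0.91 | 140/182 = 0.77 |
| 28 | 28/84 = 33% | 168/196 = 0.86 | 168/252 = 0.67 |

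This is the strongest form of the selection, because A6.6 is zero in ITT.

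**3. With disagreement and sinus elevation (simulation).** All inputs are assumed: six sites per subject, normal heights, within-subject SD 1.5 mm, reading error SD 0.5 mm, and augmentation needed below 7.0 mm (6.6 mm implant) or 8.5 mm (8.0 mm implant). The last column of settings is the number of sites of 5 to 7 mm allowed per ITT subject. It mimics the internal sinus elevation in 5.1.3, which requires at least 5 mm in native bone.

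| Mean height, between-subject SD (mm) | Sites allowed | Share excluded | R_ITT | R_all |
|---|---|---|---|---|
| 12, 1.5 | 0 | 5% | 0.92 | 0.80 |
| 12, 1.5 | 2 | 1% | 0.83 | 0.80 |
| 12, 2.5 | 0 | 14% | 0.91 | 0.62 |
| 12, 2.5 | 2 | 5% | 0.76 | 0.62 |
| 10, 1.5 | 0 | 29% | 0.90 | 0.66 |
| 10, 1.5 | 2 | 8% | 0.75 | 0.66 |

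Allowing the elevation shrinks the gap without removing it. In another assumed grid, restricted to settings with under 10% excluded, the median gap was 9 points (height only), 10 points (adding a 5.5 mm width need) and 4 points (adding a 6.5 mm width need).

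**4. Criterion.** The two width statements in 5.1.2 give 3.5 + 2×1.5 = 6.5 mm and 3.5 + 2×1.0 = 5.5 mm. On height, 0.5 mm subcrestal placement (5.1.3) gives 6.6 + 0.5 = 7.1 mm, against the 7 mm minimum. An evaluator using 6.5 mm would count eligible sites 5.5 to 6.5 mm wide as needing augmentation at both lengths, which lowers the ratio in either set.

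**5. Interval.** With 56 subjects and assumed within-subject correlations of 0.3 and 0.6, the variance of the ratio in all scanned subjects was 1.1 to 1.65 times p(1 − p)/A8.0. The standard error is then understated by a factor of √1.1 = 1.05 to √1.65 = 1.28. Nominal 95% intervals covered about 87 to 93% (normal approximation) or 89 to 95% (exact). In an ITT setting where only height matters and few sites need augmentation at 6.6 mm, the variance ratio was 0.96 to 1.07, so independence costs little there. In that setting, however, an interval from resampling subjects covered only 83 to 92%. A subject-level t interval for the paired difference covered 93 to 95%.

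**The case against.** The strongest reply is that all scanned subjects is the more natural reading. The file goes to the evaluator at Visit 2, the data cut follows Visit 2, and ITT membership cannot be known until Visit 3. A virtual plan is arguably not treatment efficacy at all. This has force, and it means the main fix may already be the intent; but the only written rule, read with the introduction to the table in 10.3, points the other way.

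Second, a gap is a bias only if all scanned subjects are the target, and the documents set no target. Subjects who can receive six 6.6 mm implants are a legitimate population, and scanned subjects have themselves been screened at Visit 1. This stands: the two sets can differ, and neither is wrong if labelled.

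Third, this is one of eight secondary outcomes, 10.3 rests all conclusions on the primary objective, and independence is stated for implants in the sample-size section. Carrying it to virtual sites is an inference, and its effect is modest.

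Three stronger readings are tempting and not supported:

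- **The ratio is 100% by construction in ITT.** That needs the evaluator's criterion to match the eligibility thresholds. The criterion is unstated, the evaluator plans independently of the investigator, and 5.1.3 lets some subjects stay in with a sinus elevation.
- **The published figure will be inflated by a large, known amount.** The set is not fixed, the share excluded is not given, and large simulated gaps mostly reflect heavy assumed exclusion. A reversal is algebraically possible: in one assumed grid it occurred in 2 of 672 settings, by less than one point.
- **The definitions contradict each other.** Section 2.2 is a summary, 6.3.2.2 gives the denominator explicitly, and 10.3 names the same quantity.

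**Conclusion.** The point holds as a gap with a predictable direction and an unknown size. The set is not named and the documents point two ways. If ITT is used and any scanned subject is excluded for bone, the ratio will tend to be higher than in all scanned subjects. The gap is zero with no exclusions. In the count example it is 2 to 7 points with about 5% excluded, 5 to 13 with about 10% and 9 to 23 with 20%. These figures rest on assumed counts and on an evaluator who agrees fully with the eligibility reading. Disagreement, a wider width criterion or sinus elevation can change them, and in the settings above elevation made the gap smaller.

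If independence is carried to this outcome, the interval is somewhat too short, with coverage of about 87 to 95% under assumed inputs. The missing augmentation criterion and the unreconciled bone figures are certain from the text. The change is worth making before the Visit 2 data cut. Nothing here affects the primary objective.

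**What to change.** - **Set.** In 10.2 and 10.3, name all consented subjects with an evaluable Visit 2 CBCT, including those later excluded for bone or not operated, as the set for this outcome. Show the numbers scanned and excluded for bone, and give ITT as a labelled supportive result.
- **Interval.** Replace the independent-site interval with a subject-level one: resample subjects for the ratio, and report the paired per-subject difference A8.0 − A6.6 with its own interval. Where few sites need augmentation at 6.6 mm, rest inference on the paired difference. It mends the interval and does not remove the dependence on the set.
- **Criterion.** State in 6.3.2.2 the augmentation criterion that the evaluator applies. The sponsor should reconcile the width and height figures in 5.1.2, 5.1.3 and 5.3.3.1; which of them is right is not a statistical question.

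The cost is a few sentences and a little more analysis, since the files already go to the evaluator at Visit 2. The downside is that the reported proportion will probably be lower than under ITT and will depend on the mix of subjects each site scans, which is why the exclusion counts must appear beside it.
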